6. Willing to be contacted by research team

Exclusion Criteria

1. Patients who do not want to participate in the telemedicine visit
2. Adults unable to read and write English. The PAM study is only in English at this time
3. Patients that do not have a home phone or home internet. This is needed to do follow up and any follow up telemedicine visits
4. Patients that do not have a smart phone or computer that can connect to the internet

PROTOCOL TITLE: Implementation of Telemedicine for patients with wounds and ulcers.

We do not plan to include:

- Pregnant women- low incidence of wounds in these patients due to PAD and DM
- Prisoners- Cannot accurately determine care and outcomes

Number of Subjects:

Rural Health Clinic A	25
Rural Health Clinic B	25
Rural Health Clinic C	25
Rural Health Clinic D	25
Rural Health Clinic E	25
Total Number of Patients	125

We plan to include 25 subjects at each of the 5 out of network clinics that are referred to the UC Davis Vascular Clinic for telehealth services for a total enrollment of 125 patients.

5) Study Timelines

The Screening and follow up of data of all patients will start approximately from 5/01/2020 – and end 12/31/2021

Review and Analysis should will be completed by approximately 06/30/2022

6) Study Endpoints

The primary endpoint for this study is time to specialty consultation.

Secondary endpoints are time to revascularization, time to other specialty consultation, time to wound healing, number of telemedicine visits, major amputation, number of hospitalizations, number of emergency room visits, and number of in person visits.

PROTOCOL TITLE: Implementation of Telemedicine for patients with wounds and ulcers.

7) Procedures Involved

Screening: Patients referred from rural clinics will be screened when they are referred to the UC Davis Vascular Clinic for telehealth services to determine if they meet the inclusion/exclusion criteria.

Enrollment/Procedures at Baseline Telehealth Visit: Patients receiving telehealth services will follow the standard operating procedures for those visits. Which includes asking new patients to complete the UCD Privacy statement for new patients and a patient activation questionnaire on the day of their telemedicine visit.

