Follow-Up Post Telehealth Visit: All patients will be contacted every 4 weeks to determine if they have had a procedure for their leg wound (revascularization) and if the wound has healed. Patients will be followed until they reach a secondary study end-point which is wound healing, amputation, or for a maximum of 12 months.

8) Withdrawal of Subjects

Patients who choose not to participate in completing a patient activation questionnaire will not be included in this QI project. Patient care is not directed in this project and is clinical driven per standard of care and standard operating procedures for the Vascular Clinic.

9) Risks to Subjects

This is a minimal risk study and the only risk foreseen is a potential breach of confidentiality which will be minimized by securing the data as outlined in the protocol.

10) Potential Benefits to Subjects

No direct benefits to the patient will occur during the data collection and review of the QI project. Future patients may receive a benefit from increased access to telehealth visits or proven to shorten time to care for patients referred from rural clinics.

PROTOCOL TITLE: Implementation of Telemedicine for patients with wounds and ulcers.

Statistical Analysis Plan: Changed as a result of COVID and removal of the comparison arm of the study

The data will be analyzed by Kaplan-Meier analysis comparing time to specialty visit for patients who underwent telemedicine visits to those who did not. Secondary outcome analysis will include chi-squared analysis of the proportion of patients that had wound healing in the telemedicine group compared to those that did not have a telemedicine visit, and Kaplan-Meier analysis of time to definitive revascularization and wound healing for patients that underwent telemedicine and were treated at UCD.

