Assuming a historical median time to a specialist consultation of 9 weeks, we will utilize a one-sample log-rank test. We want a sample large enough to detect a hazard ratio (HR) of 3.0 or higher. An HR of 3.0 indicates that at any time, three times as many specialists will consult many patients with telemedicine consultations compared to in-person consultations. A two-sided, one-sample log-rank test calculated from a sample of 24 individuals achieves 89.2% power at a 0.05 significance level to detect a hazard ratio of 3.0 when the median time to consultation of the historical control group is 9 weeks. The probability that a patient experienced a specialist consultation during the study is 0.44. The expected number of events during the study is 11. The time to specialist consultation is likely distributed by the Weibull distribution (shape parameter 1) by both groups (telemedicine and historical controls).

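### The 0.44 event probability, 11 events and 89.2% power imply about 2.5 weeks of observation per patient (no dropout), a window stated nowhere; the primary endpoint's window needs defining and the figures recomputing.

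*Combined protocol and SAP*

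**What the plan says.** The Statistical Analysis Plan sizes the primary comparison with a two-sided one-sample log-rank test at the 0.05 level: 24 patients, historical median 9 weeks, hazard ratio 3.0, power 89.2%. It adds "The probability that a patient experienced a specialist consultation during the study is 0.44" and "The expected number of events during the study is 11", and takes the times to be "likely distributed by the Weibull distribution (shape parameter 1) by both groups", that is, exponential. It gives no accrual time, follow-up time or dropout rate.

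The other sections supply these periods and events:

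- Section 6, Study Endpoints: "The primary endpoint for this study is time to specialty consultation". No starting point, window or censoring rule follows.
- Section 5, Study Timelines: screening and "follow up of data of all patients will start approximately from 5/01/2020", ending 12/31/2021.
- Section 7, Procedures Involved, baseline visit: new patients complete "a patient activation questionnaire on the day of their telemedicine visit".
- Section 7, follow-up after the telehealth visit: "All patients will be contacted every 4 weeks to determine if they have had a procedure for their leg wound", and "Patients will be followed until they reach a secondary study end-point which is wound healing, amputation, or for a maximum of 12 months".

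**The concern.** A threefold hazard against a 9-week median puts the telemedicine median at 3 weeks. In a study lasting many months almost every patient should then have a consultation, yet the plan expects fewer than half to have one. At 0.44, 24 × 0.56 = 13.4, so about 13 of 24 telemedicine patients would finish without seeing a specialist, in a project whose enrolment procedures take place at the telehealth visit.

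Two things are at stake. The stated event probability, event count and power cannot be reproduced from the stated inputs. And the gap behind them is not confined to sample size: without an origin, an event definition and a censoring rule, the primary time-to-event analysis can be run in several ways, and the choice could be made after the data are seen.

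**Working it through.** **Inputs, all from the Statistical Analysis Plan.** Historical median 9 weeks; hazard ratio 3.0; Weibull shape 1; n = 24; two-sided 0.05.

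**Hazards.** Historical: ln 2 / 9 = 0.0770 per week. Telemedicine: 3 × 0.0770 = 0.2310 per week, median 3 weeks.

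**What 0.44 implies.** With exponential times, expected events per patient equal the hazard times the mean time at risk, whatever the censoring. So mean time at risk = 0.44 / 0.2310 = 1.90 weeks. For a fixed window t without dropout, 1 − exp(−0.2310 t) = 0.44, so t = −ln(0.56) / 0.2310 = 2.51 weeks. Rounding of 0.44 (0.435 to 0.445) allows 2.47 to 2.55 weeks.

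**Reproducing the plan's figures.** Let v1 be the event probability and v0 = v1/3 the mean historical cumulative hazard per patient. Using the null variance (expected events), power = Φ[(√n (v1 − v0) − 1.96 √v0) / σ1], where σ1 is the exact standard deviation, under the alternative, of one patient's observed minus expected events.

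- Fixed 2.51 weeks: v1 = 0.440, v0 = 0.1467, σ1 = 0.550. Events = 24 × 0.44 = 10.56. Power = Φ[(1.437 − 0.751) / 0.550] = 89.4%.
- Accrual 1 week plus follow-up 2 weeks: v1 = 0.4375, v0 = 0.1458, σ1 = 0.549. Events = 10.5. Power = Φ[(1.429 − 0.748) / 0.549] = 89.2%.

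The second set matches all three stated figures. The 1 and 2 are back-solved and therefore an inference; the 1.90 weeks is not. Other readings fail. Taking 0.44 as the probability under the historical hazard gives 19.8 events and 99.9% power, and inverting the hazard ratio to 1/3 gives 97.8% power.

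**Comparison with the protocol's periods.** From 5/01/2020 to 12/31/2021 is 609 days, or 87.0 weeks. The shortest interval in the follow-up plan, the 4-week contact, is already longer than 2.5 weeks. Same n and hazard ratio, no dropout:

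| Observation per patient | Event probability | Events | Power, null variance | Power, averaged variance |
|---|---|---|---|---|
| Stated in the plan | 0.44 | 11 | 89.2% | not given |
| 1 week accrual + 2 weeks | 0.4375 | 10.5 | 89.2% | 75.0% |
| 4 weeks | 0.60 | 14.5 | 97.0% | 89.5% |
| 8 weeks | 0.84 | 20.2 | 99.9% | 99.2% |
| 9 weeks | 0.875 | 21.0 | 99.98% | 99.6% |
| Uniform entry over 87 weeks, no minimum follow-up | 0.95 | 22.8 | >99.9% | >99.9% |

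The averaged variance is the mean of observed and expected events. With so few events the formula is approximate. Simulation with the null variance gives 88.9% (1 + 2 weeks), 95.6% (4 weeks), 99.7% (9 weeks) and above 99.9% (87-week entry).

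**If the telehealth visit is itself the consultation.** Section 7 places the questionnaire on the day of that visit, and section 8 leaves out patients who do not complete it. Every included patient would then have the event, and the probability would be 1, not 0.44.

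**The case against.** The best defence is that nothing has been miscalculated. The three figures agree, and what is missing is a set of inputs. The 12-month follow-up starts after the telehealth visit and serves secondary endpoints, and the 87 weeks are a study calendar, not one patient's time at risk. On this view the documents leave the primary window undefined and do not contradict it. That is a fair description of those two periods, but it does not rescue 0.44, which the plan gives as a probability over the study. No period or event that the documents offer produces it.

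Dropout could also lower the probability. Windows of 4, 9 or 52 weeks with exponential dropout tuned to 0.44 give about 10.6 events and 90.0% to 90.9% power. That requires a dropout half-life of about 2.4 to 3.5 weeks, and it would be a further unstated assumption. What stands is that the 2.5-week figure must carry its no-dropout condition.

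It also stands that the direction of the error depends on the test. With the null variance, which reproduces 89.2%, any longer window raises power. With the averaged variance, power reaches 89.2% only at about 4 weeks, and at the 1 + 2-week inputs it is 75.0%.

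Finally, no recruitment decision turns on these figures: section 4 plans 125 patients, and even at 0.44 that number gives power close to 100% at a hazard ratio of 3.0. This is true, and it limits the severity. The undefined endpoint remains.

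**Conclusion.** The concern holds. The stated 0.44, 11 events and 89.2% are mutually consistent but belong to a study with 1.90 weeks at risk per patient, or a 2.5-week window without dropout, and the documents describe no such study. For observation of 9 weeks or more the plan's own inputs give an event probability of 0.875 or higher, at least 21 of 24 patients with events, and power above 99% under either variance. If the telehealth visit counts as the event, the probability is 1.

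This rests on the plan's exponential model, 9-week median and hazard ratio of 3.0, and on no dropout, since none is stated. For windows of about 4 weeks or longer with little dropout the stated figures understate events and do not overstate power, so the sample is not too small on this account. The point should be corrected because the power statement for the primary endpoint cannot be reproduced, and because the missing window, origin and event definition also govern the primary analysis.

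**What to change.** 1. In section 6 and the Statistical Analysis Plan, define the time origin for time to specialty consultation (for example, date of referral), the event, the observation window and the censoring rule. Say explicitly whether the telehealth visit counts as the event.
2. Redo the one-sample log-rank calculation with accrual, follow-up and median all in weeks.
3. State those inputs, any assumed dropout, and the variance used in the test statistic. For short windows, confirm the power by simulation.
4. Replace 0.44, 11 and 89.2% with the results. The values depend on the window chosen; for about two months or more with little dropout, expect an event probability of roughly 0.85 or higher and power above 99% at a hazard ratio of 3.0 with 24 patients.

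The cost is one definition, one recalculation and one paragraph of wording. Enrolment and the choice of test do not change.
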